8.3.2. Analyses of Safety

Safety analyses will be summarized with descriptive statistics and performed on the Safety population.

For all phases, safety will be assessed by the incidence of treatment-emergent MAAEs, SAEs, solicited local and systemic reactogenicity AEs, and unsolicited AEs for the time period of interest, overall and by grade according to the Guidance for Industry: Toxicity Grading Scale for Healthy Adult and Adolescent Volunteers Enrolled in Preventive Vaccine Clinical Trials (2007). Clinically significant changes in safety laboratory tests and vital signs will be summarized.

8.3.3. Analyses of Immunogenicity

In phase 1 and phase 2, immunogenicity endpoints will be summarized using descriptive statistics for the immunogenicity population. Data will be log-transformed for analyses, as appropriate. GMTs and their associated 95% confidence intervals (CIs) will be computed based by exponentiation of the corresponding log-transformed means and 95% CIs at each time point.

8.4. Sample Size

The sample sizes for phases 1 and 2 are not based on statistical justification. A total of 60 participants will be treated in phase 1 (10 participants for each cohort). A total of 120 participants will be randomized in phase 2 to receive either the control arm or one of the experimental arms (30 participants/arm).

8.5. Randomization

In the phase 2, 30 participants will be randomly assigned to each arm based a 1:1:1:1 randomization ratio. The phase 2 randomization will be stratified by age (18 to 55 years or > 55 years), by previous infection (previously infected or not), and by HIV status (positive or negative). The randomization for the phase 2 portion of the study will be performed by site personnel through the study EDC system.

9. INVESTIGATOR RESPONSIBILITIES

Investigator responsibilities are set out in the ICH Guideline for GCP and in the local regulations. Sponsor staff or an authorized representative will evaluate and approve all Investigators who in turn will select their staff.

The Investigator should ensure that all persons assisting with the study are adequately informed about the protocol, amendments, and study treatments as well as study-related duties and functions. The Investigator should maintain a list of sub-Investigators and other appropriately qualified persons to whom he or she has delegated significant study-related duties.

The Investigator is responsible for keeping a record of all participants who sign an informed consent document and are screened for entry into the study. Participants who fail screening must have the reason(s) recorded in the participant's source documents.

The Investigator or a designated member of the Investigator's staff, must be available during monitoring visits to review data, resolve queries and allow direct access to participant records (eg, medical records, office charts, hospital charts, and study-related charts) for source data verification. The Investigator must ensure timely and accurate completion of CRFs and queries.

10. REGULATORY CONSIDERATIONS

10.1. Good Clinical Practice

The procedures set out in this study protocol pertaining to the conduct, evaluation, and documentation of this study are designed to ensure that the Sponsor, its authorized representative(s), and Investigator(s) abide by GCP, as described in the ICH E6 R2 and in accordance with the general ethical principles outlined in the Declaration of Helsinki. The study will receive approval from an IRB/IEC prior to commencement. The Investigator will conduct all aspects of this study in accordance with applicable national, state, and local laws of the pertinent regulatory authorities.

10.2. Participant Information and Informed Consent

The Investigator must obtain written informed consent from the participant or a legal representative prior to performing any study-related procedures. Each Investigator has both ethical and legal responsibility to ensure that the participant's being considered for inclusion in this study are provided a full explanation of the protocol and the roles and responsibilities of the participant for participation in the study.

Documentation that written informed consent was obtained prior to the study participant's entry into the study and of the informed consent process should be recorded in the study participant's source documents, including the date. The original informed consent document signed and dated by the study participant and by the person consenting the study participant prior to the study participant's entry into the study must be maintained in the Investigator's study files and a copy given to the study participant. In addition, if a protocol is amended and the amendment(s) impact the content of the informed consent, the informed consent document must be revised. Study participants participating in the study when the amended protocol is implemented must be re-consented with the revised version of the informed consent document. The revised informed consent document signed and dated by the study participant and by the person consenting the study participant must be maintained in the Investigator's study files and a copy given to the study participant.

10.3. Confidentiality

The Sponsor affirms the participant's right to protection against invasion of privacy and to be in compliance with ICH and other local regulations (whichever is most stringent). The Sponsor requires the Investigator to permit Sponsor and/or their designated representatives and, when necessary, representatives from regulatory authorities, to review and/or copy any medical records relevant to the study in accordance with local laws.

Should direct access to medical records require a waiver or authorization separate from the participant's signed informed consent document, it is the responsibility of the Investigator to obtain such permission in writing from the appropriate individual.

Participants will be identified only by unique participant numbers in CRFs.

10.4. Protocol Amendment

Any amendment to this protocol must be approved by the Sponsor or its designated clinical research physician/medical monitor. Amendments will be submitted to the IRB/IEC for written approval. Written approval must be obtained before implementation of the amended version occurs. The written signed approval from the IRB/IEC should specifically reference the Investigator name, protocol number, study title and amendment number(s) that is applicable. Amendments that are administrative in nature do not require IRB/IEC approval but will be submitted to the IRB/IEC for information purposes.

10.5. Institutional Review Board/Independent Ethics Committee Review and Approval

The Investigator must obtain IRB/IEC approval for the investigation. Initial IRB/IEC approval, and all materials approved by the IRB/IEC for this study, including the participant consent form and recruitment materials, must be maintained by the Investigator and made available for inspection.

The final study protocol, including the final version of the ICF, must be approved or given a favorable opinion in writing by an IRB or IEC as appropriate. The Investigator must submit written approval to the Sponsor before he or she can enroll any participant into the study.

The Investigator is responsible for informing the IRB or IEC of any amendment to the protocol in accordance with local requirements. In addition, the IRB or IEC must approve all advertising used to recruit participants for the study. The protocol must be re-approved by the IRB or IEC upon receipt of amendments and at least annually, as local regulations require.

The Investigator is also responsible for providing the IRB/IEC with reports of any reportable serious adverse drug reactions from any other study conducted with study regimen. The Sponsor will provide this information to the Investigator.

Progress reports and notifications of serious adverse drug reactions will be provided to the IRB or IEC in accordance with local regulations and guidelines.

10.6. Closure of Study

The Sponsor reserves the right to terminate this study at any time for reasonable medical or administrative reasons. Any premature discontinuation will be appropriately documented in accordance with local requirements (eg, IRB/IEC, regulatory authorities).

In addition, the Investigator or the Sponsor has the right to discontinue a single site at any time during the study for medical or administrative reasons such as:

- Unsatisfactory enrollment.
- GCP noncompliance.
- Inaccurate or incomplete data collection.
- Falsification of records.
- Failure to adhere to the study protocol.

11. DATA HANDLING AND RECORDKEEPING

11.1. Data/Documents

The Investigator must ensure that the records and documents pertaining to the conduct of the study and the distribution of the study regimen are complete, accurate, filed, and retained. Examples of source documents include hospital records, clinic and office charts, laboratory notes, memoranda, participant's diaries or evaluation checklists, dispensing records, recorded data from automated instruments, copies or transcriptions certified after verification as being accurate copies, microfiche, x-ray film and reports, and records kept at the pharmacy and the laboratories, as well as copies of CRFs and any study data/source documents that have been stored to a flash drive, portable hard drive, or CD-ROM.

11.2. Data Management

Study data will be collected via an Electronic Data Capture (EDC) system and will be managed through the use of programmed electronic edit checks. Data discrepancies will be brought to the attention of the clinical team and investigational site personnel, if necessary. An audit trail of the resolution of data discrepancies will be maintained in the EDC system.

11.3. Inspection of Records

The Sponsor will be allowed to conduct site visits to the investigation facilities for the purpose of monitoring any aspect of the study. The Investigator agrees to allow the monitor to inspect the drug storage area, investigational agent tocks, drug accountability records, participant charts and study source documents, and other records relative to study conduct.

11.4. Retention of Records

Essential documents must be retained by the Investigator for a minimum of 2 years after the last approval of a marketing application in an ICH region and until there are no pending or contemplated marketing applications in an ICH region, or at least 2 years have elapsed since the formal notification to regulatory authorities of discontinuation of clinical development of the IP; and for a period of at least 3 years after the Sponsor notifies the Investigator that the final report has been filed with regulatory authorities. The Investigator must retain these documents for the time period described above or in accordance with local laws or requirements, whichever is longer. Essential documents include, but are not limited to, the following:

- Signed informed consent documents for all participants.
- Participant identification code list, screening log (if applicable), and enrollment log.
- Record of all communications between the Investigator and the IRB/IEC.
- Composition of the IRB/IEC.
- Record of all communications between the Investigator, Sponsor, and their authorized representative(s).

- List of sub-Investigators and other appropriately qualified persons to whom the Investigator has delegated significant study-related duties, together with their roles in the study, curriculum vitae, and their signatures.
- Copies of CRFs (if paper) and of documentation of corrections for all participants.
- Investigational agent accountability records.

If it becomes necessary for the Sponsor or the Regulatory Authority to review any documentation relating to the study, the Investigator must permit access to such records.

Approved

12. QUALITY CONTROL AND QUALITY ASSURANCE

All aspects of the study will be carefully monitored by the Sponsor or its authorized representative(s) to ensure compliance with applicable government regulations with respect to current ICH GCP, the study protocol, and all relevant standard operating procedures (SOPs).

12.1. Audits and Inspections

The Investigator and/or institution will allow monitors and auditors direct access to source documentation to perform verification duties. Authorized representatives of the Sponsor, a regulatory authority, or an IRB/IEC may visit the site to perform audits or inspections, including source data verification. The purpose of a Sponsor audit or inspection is to systematically and independently examine all study-related activities and documents to determine whether these activities were conducted and data were recorded, analyzed, and accurately reported in accordance with the protocol, GCP guidelines of the ICH, and any applicable regulatory requirements. The Investigator is required to permit direct access to the facilities where the study took place, source documents, CRFs, and applicable supporting records of study participant participation for audits and inspections by company authorized representatives, regulatory authorities, and IRB/IECs. The Investigator should make every effort to be available for the audits and/or inspections. The Investigator should contact the Sponsor immediately if contacted by a regulatory agency about an inspection.

13. PUBLICATION POLICY

The results of this study may be published in a medical journal, presented at a medical congress, or used for teaching purposes. Additionally, this study and its results may be submitted for inclusion in all appropriate health authority study registries, as well as publication on health authority study registry websites, as required by local health authority regulations.

Authorship will be based on the International Committee of Medical Journal Editors criteria for authorship:

4. Substantial contributions to the conception or design of the work; or the acquisition, analysis, or interpretation of data for the work; and
5. Drafting the work or revising it critically for important intellectual content; and
6. Final approval of the version to be published/presented; and
7. Agreement to be accountable for all aspects of the work in ensuring that questions related to the accuracy or integrity of any part of the work are appropriately investigated and resolved.

All four conditions must be met to qualify for authorship

The Sponsor must be informed of any plans to publish the results of this study and has the right to review any publication (eg, manuscript, abstract, oral/slide presentation, book chapter) resulting from this study before it is submitted/presented.

APPENDIX 1. SAMPLE DIARY FOR SOLICITED EVENTS

STUDY NUMBER*: _____

Patient Number*		Date of Vaccine Administration	/	/	/	*To be completed by the site		
-----------------	--	--------------------------------	---	---	---	------------------------------	--	--

Please answer all questions below daily for 7 days, beginning with day of treatment. Be sure to bring back this completed diary to your next clinic visit.

Intramuscular: Solicited local AEs	Instructions	Date / /						
1. Is there redness at the injection site?	Check:  Yes or  No If yes, measure longest diameter in cm	 Yes or  No _____ cm	 Yes or  No _____ cm	 Yes or  No _____ cm	 Yes or  No _____ cm	 Yes or  No _____ cm	 Yes or  No _____ cm	 Yes or  No _____ cm
2. Is there firmness at the injection site?	Check:  Yes or  No	 Yes or  No	 Yes or  No	 Yes or  No	 Yes or  No	 Yes or  No	 Yes or  No	 Yes or  No
3. Is there swelling at the injection site?	Check:  Yes or  No If yes, measure longest diameter in cm	 Yes or  No _____ cm	 Yes or  No _____ cm	 Yes or  No _____ cm	 Yes or  No _____ cm	 Yes or  No _____ cm	 Yes or  No _____ cm	 Yes or  No _____ cm
4. Have you experienced any pain or itching at the injection site?	Check:  Pain  Itch or  No Pain/Itch Circle mild, moderate or severe	 Pain  Itch Mild Mild Mod Mod Severe Severe  No Pain/Itch	 Pain  Itch Mild Mild Mod Mod Severe Severe  No Pain/Itch	 Pain  Itch Mild Mild Mod Mod Severe Severe  No Pain/Itch	 Pain  Itch Mild Mild Mod Mod Severe Severe  No Pain/Itch	 Pain  Itch Mild Mild Mod Mod Severe Severe  No Pain/Itch	 Pain  Itch Mild Mild Mod Mod Severe Severe  No Pain/Itch	 Pain  Itch Mild Mild Mod Mod Severe Severe  No Pain/Itch
5. Have you taken or applied any medication for injection site pain or itching?	Check:  Yes or  No Provide name of medication(s)	 Yes or  No Name(s):						
6. Is there tingling or numbness at the injection site?	Check:  Yes or  No	 Yes or  No	 Yes or  No	 Yes or  No	 Yes or  No	 Yes or  No	 Yes or  No	 Yes or  No
7. Is there bleeding at the injection site?	Check:  Yes or  No	 Yes or  No	 Yes or  No	 Yes or  No	 Yes or  No	 Yes or  No	 Yes or  No	 Yes or  No
8. Is there bruising at the injection site?	Check:  Yes or  No	 Yes or  No	 Yes or  No	 Yes or  No	 Yes or  No	 Yes or  No	 Yes or  No	 Yes or  No

Grading Injection Site Pain or Itching:

Mild – Noticeable, does not interfere with activity

Moderate – Interferes with activity, limiting activities of daily life

Severe – Severely limiting self-care activities of daily living, incapacitating

STUDY NUMBER*: _____

Patient Number*		Date of Vaccine Administration	/	/	/	*To be completed by the site		
-----------------	--	--------------------------------	---	---	---	------------------------------	--	--

Please answer all questions below daily for 7 days, beginning with day of treatment. Be sure to bring back this completed diary to your next clinic visit.

| Solicited systemic AEs | Instructions | Date / / |
|---|---|---|---|---|---|---|---|---|
| 1. Have you experienced any chills? | Check:
 Yes or  No
If yes, tell us if the chills are mild, moderate or severe |  Yes or  No
Mild
Moderate
Severe |
| 2. Have you experienced nausea? | Check:
 Yes or  No
If yes, tell us if the nausea is mild, moderate or severe |  Yes or  No
Mild
Moderate
Severe |
| 3. Have you experienced vomiting? | Check:
 Yes or  No
If yes, tell us if the vomiting is mild, moderate or severe |  Yes or  No
Mild
Moderate
Severe |
| 4. Have you experienced diarrhea? | Check:
 Yes or  No
If yes, tell us if the diarrhea is mild, moderate or severe |  Yes or  No
Mild
Moderate
Severe |
| 5. Have you experienced any headache? | Check:
 Yes or  No
If yes, tell us if the headache is mild, moderate or severe |  Yes or  No
Mild
Moderate
Severe |
| 6. Have you experienced any fatigue? | Check:
 Yes or  No
If yes, tell us if the fatigue is mild, moderate or severe |  Yes or  No
Mild
Moderate
Severe |
| 7. Have you experienced any muscle pain? | Check:
 Yes or  No
If yes, tell us if the muscle pain is mild, moderate or severe |  Yes or  No
Mild
Moderate
Severe |
| 8. Have you experienced any abdominal discomfort/pain? | Check:
 Yes or  No
If yes, tell us if the abdominal discomfort/pain is mild, moderate or severe |  Yes or  No
Mild
Moderate
Severe |
| 9. Have you experienced any joint pain? | Check:
 Yes or  No
If yes, tell us if the joint pain is mild, moderate or severe |  Yes or  No
Mild
Moderate
Severe |

STUDY NUMBER*:

| Solicited systemic AEs | Instructions | Date / / |
|---|---|---------------------------------------|---------------------------------------|---------------------------------------|---------------------------------------|---------------------------------------|---------------------------------------|---------------------------------------|
| 10. Record your daily temperature upon waking (do not drink anything 5 minutes before taking your temperature) | Fill in the temperature and time:
If your temperature is 38°C for more than 24 hours, call your doctor | ____ °C
Time:
____ :
AM / PM |

Grading Chills:

Mild: Mild sensation of cold, shivering, chattering of teeth
 Moderate: Moderate tremor of entire body, medication taken
 Severe: Prolonged or severe, does not respond to medication

Grading Nausea and Vomiting:

Mild: No interference with activity or 1 – 2 episodes/24 hours
 Moderate: Some interference with activity or > 2 episodes/24 hours
 Severe: Prevents daily activity, requires outpatient IV hydration

Grading Diarrhea:

Mild: 2 – 3 loose stools or < 400 gms/24 hours
 Moderate: 4 – 5 stools or 400 – 800 gms/24 hours
 Severe: 6 or more watery stools or > 800 gms/24 hours or requires outpatient IV hydration

Grading Headache:

Mild: No interference with activity
 Moderate: Repeated use of non-narcotic pain reliever > 24 hours or some interference with activity
 Severe: Significant; any use of narcotic pain reliever or prevents daily activity

Grading Fatigue:

Mild: No interference with activity
 Moderate: Some interference with activity
 Severe: Significant; prevents daily activity

Grading Muscle Pain:

Mild: No interference with activity
 Moderate: Some interference with activity
 Severe: Significant; prevents daily activity

Grading Abdominal Discomfort/Pain:

Mild: No interference with activity
 Moderate: Some interference with activity
 Severe: Significant; prevents daily activity

Grading Joint Pain:

Mild: No interference with activity
 Moderate: Some interference with activity
 Severe: Significant; prevents daily activity

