3.4.1.1. Primary Endpoints

- Incidence of MAAEs and SAEs through 1 week post final vaccine administration
- Incidence of MAAEs and SAEs through 30 days post final vaccine administration
- Incidence of MAAEs and SAEs through 6 months post final vaccine administration
- Incidence and severity of solicited local reactogenicity AEs through 1 week after each vaccine administration
- Incidence and severity of solicited systemic reactogenicity AEs through 1 week after each vaccine administration
- Incidence and severity of unsolicited AEs through 1 week post final vaccine administration

- Incidence and severity of unsolicited AEs through 30 days post final vaccine administration
- Incidence of abnormal changes of laboratory safety examinations
- Changes in vital signs

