6.2. Baseline/Screening Assessments

The following procedures and evaluations are to be performed at baseline/screening:

- Study introduction and written informed consent obtained prior to performing any study assessments or procedures (screening visit and/or protocol amendments that affect study assessments or participant treatment).
- Inclusion/exclusion
- Demographics and complete medical history, including current symptoms and COVID-19-related symptoms
- Tuberculosis screening
- History of COVID-19
- Confirmation of contraceptive measures
- Physical exam
- Vital signs
- Concomitant medications
- Blood draw and urine collection for clinical laboratories
- Biospecimen collection for SARS-CoV-2 testing
- Pregnancy test (serum [β -human chorionic gonadotropin] or urine): The pregnancy test result will be confirmed as negative immediately prior to vaccine administration. A positive pregnancy test occurring while the participant is participating in the study is considered an immediately reportable event.

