7.2. Definition of Adverse Events

AEs and grading criteria listed below are consistent in definitions in 21 CFR 312.32.

An AE is any noxious, unintended, or untoward medical occurrence that may appear or worsen in a participant during the study. It may be a new intercurrent illness, a worsening concomitant illness, an injury, or any concomitant impairment of the participant's health, including laboratory test values (as specified by the criteria below), regardless of etiology. A diagnosis or syndrome should be recorded on the AE page of the case report form (CRF) rather than the individual signs or symptoms of the diagnosis or syndrome.

An abnormal laboratory value is considered to be an AE if the abnormality:

- Results in discontinuation from the study;
- Requires treatment, modification/interruption of the study treatment dose, or any other therapeutic intervention; or
- Is judged to be of significant clinical importance.

Regardless of the severity grade, only laboratory abnormalities that fulfill a seriousness criterion need to be documented as an SAE.

If a laboratory abnormality is one component of a diagnosis or syndrome, then only the diagnosis or syndrome should be recorded as an AE. If the abnormality was not a part of a diagnosis or syndrome, then the laboratory abnormality should be recorded as an AE.

An AE with medically-attended visits (either in person or telemedicine visit) that are not routine visits for physical examination or vaccination, such as visits for hospitalization, an emergency room visit, or an otherwise unscheduled visit to or from medical personnel (medical doctor) for any reason, will be documented as a MAAE. MAAEs can also be SAEs and will follow the same serious adverse event criteria and collection guidelines noted in [Section 7.3](#).

Duration and Frequency for Collecting AE and SAE Information

In the phase 1 and phase 2 studies, solicited AEs will be recorded by the investigator for 7 days after each dose. In the phase 1 and phase 2 studies, unsolicited AEs will be recorded from the time of first dose of study treatment until 30 days after study intervention. All MAAEs and SAEs will be recorded by the investigator from the time of first dose of study treatment until 6 months after study intervention. For MAAEs/SAEs that are considered related to study treatment, those events should be reported at any time regardless of vaccine administration date or end of study visit date.

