7.5.1. Reporting Procedures for Adverse Events

Any AE (as defined in [Section 7.2](#)) should be reported as an AE on the AE page of the CRF and in the participant's source documents.

Any medical condition that is present at the study participant's screening visit will be considered as baseline and not reported as an AE; however, if the study participant's condition deteriorates at any time during the study, it will be recorded as an AE.

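### No record of the solicited systemic symptoms is specified before each injection, so a symptom already present that day may be counted as reactogenicity

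*Combined protocol and SAP*

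**What the plan says.** **Diary.** Appendix 1 instructs: "Please answer all questions below daily for 7 days, beginning with day of treatment". The systemic items take the form "Have you experienced any headache", answered yes or no with a severity. There is no pre-dose column, no onset time and no restriction to the period since the injection. The temperature item asks for a reading on waking, so day-of-treatment entries are not confined to the hours after dosing.

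**Baseline.** Section 6.2 lists "Demographics and complete medical history, including current symptoms and COVID-19-related symptoms" among the screening procedures, and Table 10 places screening on day -5 to -1. Section 7.5.1 then states: "Any medical condition that is present at the study participant's screening visit will be considered as baseline and not reported as an AE", unless the condition deteriorates.

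**Day of dosing.** The Table 10 footnotes fix pre-dose timing for the urine, SARS-CoV-2 and immunogenicity samples and for the pregnancy test. Days 1 and 29 also carry in-office AE collection, COVID-19 symptom inquiry, vital signs, concomitant medications and a targeted examination if indicated. None of these is stated to precede the injection, and none is tied to the Appendix 1 list.

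**Definition and analysis.** Under section 7.2 an AE is something that "may appear or worsen in a participant during the study". Section 8.3.2 says "safety will be assessed by the incidence of treatment-emergent MAAEs, SAEs, solicited local and systemic reactogenicity AEs", among other events. Section 3.4.1.1 makes "Incidence and severity of solicited systemic reactogenicity AEs through 1 week after each vaccine administration" a phase 1 primary endpoint. Section 3.4.2.2.1 makes it secondary in phase 2.

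**The concern.** Headache, fatigue, nausea, and muscle or joint pain are common without any vaccine. Section 3.1 also admits people with medically stable chronic diseases. A participant who woke with a headache on day 1 can truthfully answer yes for that day, and the form gives the analyst no means of telling that answer from a reaction to the injection.

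Phase 1 has no control group from which to estimate the background. Each cohort has 10 participants, and section 3.1 says that phase 1 determines the phase 2 dose levels. In phase 2 no statistical comparison of the arms is planned (section 8.3.1), so each arm's own rate is the reported result. A pre-dose symptom state that was not recorded cannot be reconstructed at analysis.

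**Working it through.** **Which rule catches which symptom**

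| Onset | What the plan provides | Could it be counted? |
|---|---|---|
| Present at screening | Baseline under 7.5.1 | No, unless it deteriorates, provided diary answers are checked against the screening record |
| After screening, before the vaccination day | Not screening baseline. A start date under 7.4.3 would be earlier than the dose, but the diary does not ask for one | Yes, if not otherwise documented |
| Vaccination day, before the injection | The start date is the vaccination day, the same as for a true reaction | Yes |
| After the injection | Solicited AE | Yes, as intended |

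For the second dose in arm 3, the screening record is more than four weeks old on day 29. Section 7.4.3 does have the investigator ask at each visit about AEs since the last one, which helps for events between the doses. It does not separate onset before and after the injection on day 29 itself.

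**Size**

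The plan states no figure to reproduce here, and section 8.4 says that the sample sizes have no statistical justification. The counts are consistent: 6 × 10 = 60 and 4 × 30 = 120.

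*Effect of one participant.* 1/10 = 10 percentage points in a phase 1 cohort; 1/30 = 3.3 points in a phase 2 arm.

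*Upper bound on the reported rate.* Let r be the true incidence and p the proportion with at least one listed systemic symptom before the injection. The documents do not give p, so 5% to 20% is an assumption. If the two are independent and every pre-dose symptom is counted, reported incidence = r + (1 − r)p.

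| r | p = 5% | p = 10% | p = 20% |
|---|---|---|---|
| 40% | 0.40 + 0.60 × 0.05 = 43% | 0.40 + 0.60 × 0.10 = 46% | 0.40 + 0.60 × 0.20 = 52% |
| 20% | 0.20 + 0.80 × 0.05 = 24% | 0.20 + 0.80 × 0.10 = 28% | 0.20 + 0.80 × 0.20 = 36% |

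*Chance that a cohort of 10 includes at least one such participant*, 1 − (1 − p)^10:
- p = 5%: 1 − 0.95^10 = 40%
- p = 10%: 1 − 0.90^10 = 65%
- p = 20%: 1 − 0.80^10 = 89%

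These are ceilings, because the existing rules would remove some cases. If they removed half (again an assumption), p would be 2.5% to 10%, and a true 40% would be reported as 0.40 + 0.60 × 0.025 = 41.5% up to 46%.

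**The case against.** The best defence is that the plan already has filters. Section 7.2 requires an event to appear or worsen, 7.5.1 removes what was present at screening, and 8.3.2 is limited to treatment-emergent events. Section 7.4.3 requires a start date, and 7.4 requires investigator evaluation of each AE. The diary is only a sample, and section 6.3.1 says that solicited AEs are also captured at visits. Further detail may sit in the separate SAP mentioned in 8.1 or in the CRF guidelines mentioned in 7.4.3. The bias also overstates reactogenicity, which is the cautious direction for safety.

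Much of this stands, and it rules out several stronger readings that a reader might infer:
- **That pre-dose symptoms are counted as reactogenicity.** The documents do not say so. They leave open how a yes on the first diary day is set against baseline, so the symptoms may be counted.
- **That symptoms are asked about only at screening.** Table 10 has AE collection and COVID-19 symptom inquiry on days 1 and 29. What is missing is a stated pre-dose timing and use of the solicited list.
- **That the safety pauses would be set off wrongly.** The related-event rules in 7.8.2 and 7.8.2.1 need a relatedness judgement, and their Grade 3 thresholds need at least three participants. An effect is possible but limited. The protection is partial, because relatedness under 7.4.2 rests largely on timing, which is the information not recorded.
- **That phase 2 comparisons are compromised.** None is planned, and randomization balances background symptoms on average. Only the descriptive rates move.

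The filters do not close the gap itself. A start date cannot split a single day, and an undefined treatment-emergent rule has no pre-dose symptom record to work from.

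**Conclusion.** The gap is real and moderate in size. The plan specifies no pre-injection record of the Appendix 1 systemic symptoms and does not limit the first diary day to the time after injection. Symptoms that began earlier that day, or after screening without other documentation, may enter the solicited systemic AE rates.

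The consequence is an upward bias in descriptive rates, chiefly in uncontrolled phase 1. At most, a true 40% would be reported as 43% to 52%. That rests on an assumed 5% to 20% pre-dose prevalence, on independence, and on no case being filtered out. The 10-point shift per misattributed participant in a cohort of 10 needs none of these assumptions.

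A reader might infer that a pre-dose check would remove all background symptoms from phase 1. It would not: those arising after the injection or on diary days 2 to 7 would still be counted, as in any uncontrolled study. The point does not undermine the trial, but the change is worth making before dosing because the information cannot be recovered later.

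**What to change.** 1. **Table 10:** add a short pre-dose record (presence and severity) of the Appendix 1 systemic items on day 1, and on day 29 for experimental arm 3.
2. **Appendix 1:** state that the day-of-treatment entry covers only the time after the injection.
3. **Section 8.3.2 and the SAP:** define a treatment-emergent solicited systemic AE as one that is new, or worse in severity, compared with that pre-dose record.
4. **Section 7.5.1:** for solicited AEs, set baseline as the last assessment before dosing, in place of the screening visit.

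The cost is a few minutes at visits that already take place, one CRF page and a line in the SAP. No visit or sample is added. If only part can be done, items 2 and 3 clarify the intent, but without item 1 there is still no pre-dose symptom record against which to apply the definition.
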